Title: Outpatient endometrial biopsy results; a quality improvement project.

Date: 4/11/2024

NCT06694246

CLINICAL AUDIT PROJECT PLAN

Please complete this project plan before starting your project.

1. Short Title of Audit: Outpatient endometrial biopsy results; a quality improvement project.

2. Details of Audit Lead

Audit Lead:	Name: [name]	Designation: Registrar
Contact details:	E-mail: [contact]	[contact]

3. Details of Audit Sponsor:

Audit Sponsor:	Name: [name]: Consultant
	Name: [name]: Head of department

4. Date plan completed: 27/10/2024

5. Rationale and objectives of the Audit:

Pipelle is the most commonly used outpatient endometrial biopsy device.

Pipelle endometrial biopsy can diagnose 90% of endometrial cancer cases.

It is one of the first line diagnostic procedure for women presenting with abnormal peri- and post-menopausal vaginal bleeding.

Insufficient samples are obtained in 5-23% of cases.

In our hospital, a retrospective analysis of all outpatient endometrial samples sent to the histopathology department from April- to October 2024 study showed an insufficient sample percentage of 32% This maybe attributed to patients, equipment, and physicians factors.

Our project aims to improve the endometrial biopsy results by Identifying these factors in our hospital setting, Implementing measures to modify them, and finally e-auditing the endometrial biopsy results after six months.

6. Based on your audit rationale how would you classify this audit?

This is an external audit  (e.g. National audit)	This is an internal audit  (e.g arising from Trust objectives/ risks/ incidents / complaints/ NICE guidelines compliance etc)
This a Division/Service priority  (e.g. part of Divisional or Team Service improvement priorities)	This is an individual clinician interest  (e.g. personal interest, personal development or as part of an educational or training programme)

7. Background and criteria that will be audited?

Evidence:

- Giuseppe Del Priore. Office-based endometrial sampling procedures. In: UpToDate, Connor RF (Ed), Wolters Kluwer. (Accessed on October 21, 2024.)

Suggested criteria (proforma items):

1. Place the patient in the dorsal lithotomy position.
2. Perform a bimanual examination, paying particular attention to the size, shape, and orientation of the uterus.
3. Insert a speculum and visualize the cervix.
4. Cleaning the cervix with antiseptic solution (eg, povidone-iodine) is performed by some clinicians, but not all. Sterile preparation in patients who are allergic to iodine is discussed separately.
5. If anesthesia is to be used, it is administered prior to any other manipulation.
6. In many patients, an endometrial sampling device can be inserted without grasping the cervix with a tenaculum. Use of a tenaculum increases patient discomfort.
7. A tenaculum should be used if the uterus is not close to axial in position. In such cases, place a tenaculum (with teeth in a horizontal position) on the anterior cervical lip and retract outwardly to straighten the cervicouterine angle. Straightening the uterine axis may reduce the risk of uterine perforation. If a tenaculum is required and a paracervical block has not been given, we may apply a local anesthetic (eg, 2% benzocaine gel or 20% benzocaine spray) to the intended site before placing the tenaculum. Directing the patient to cough while simultaneously applying the tenaculum may also decrease discomfort. Patients scheduled for sampling may be advised to take an NSAID prior to arriving at the clinic.
8. Using steady and moderate pressure, slowly insert the sampling device through the cervical os and on to the uterine fundus. Stop when resistance is met.
9. If the device will not pass through the cervix, attach a tenaculum (if not already in place), and use a series of small (1 to 4 mm) Hegar or similar dilators to gently dilate the canal. An Allis clamp rather than a single-tooth tenaculum may offer some advantages (eg, less bleeding).
10. Many devices are marked with centimeters, so the device can be used to measure the uterine depth. Average uterine length is 6 to 8 cm.
11. Stabilize the sheath with one hand and pull the piston out as far as possible to create suction.
12. Move the device tip along the endometrial surface using a corkscrew rotation combined with a repeating cephalic-caudal motion while maintaining suction.
13. Remove the device when the entire cavity has been sampled. Expel the specimen into a formalin container. If there appears to be insufficient tissue for diagnosis, perform a second pass with the device. The same device may be used if it has not been contaminated; it should not have touched the formalin.
14. Remove the tenaculum, if present. Most bleeding can be controlled with pressure via cotton swabs or a sponge stick. If bleeding persists, use ferric subsulfate (Monsel) solution or silver nitrate sticks to cauterize the site.

Side effects and complications:

1. The most common side effect of endometrial sampling is cramping, which subsides rapidly after the procedure is completed. Cramping tends to be more severe with the higher pressure suction devices than low-pressure devices because the former is more rigid, the suction is greater, and larger samples are removed. Many patients will experience light vaginal bleeding or spotting for several days following the procedure.

2. Vasovagal reactions are not uncommon during endometrial sampling. Such reactions can generally be prevented by allowing the patient to eat and drink before the procedure and by minimizing pain through use of analgesics and, if necessary, local anesthesia. The risk of uterine perforation is approximately 1 to 2 per 1000 procedures.
3. Rare complications include excessive uterine bleeding (especially with undiagnosed coagulopathies), uterine perforation (risk, 0.1 to 1.3 percent), pelvic infection, and bacteremia (including sepsis and endocarditis).

Contraindications:

1. The only absolute contraindication to endometrial sampling is the presence of a viable and desired pregnancy
2. A bleeding diathesis is a relative contraindication since bleeding may be excessive in such patients
3. In the presence of acute vaginal, cervical, or pelvic infection, the procedure should be deferred, if possible, until the infection has been treated. This does not apply to clinical situations in which the indication for the biopsy is to evaluate for a subclinical infection or perform microbiologic and histologic studies.
4. In rare instances, in which endometrial sampling needs to be performed in a patient with cervical cancer, an obstructing cervical lesion may be a relative contraindication in some patients due to increased risk of bleeding or uterine perforation. Imaging may obviate the need for endometrial sampling in this circumstance.
5. Sampling can be performed with an intrauterine device in place. In our practice, we have done so without complications

N.B.:

- **One approach to improving the tissue adequacy rate** is by using a technique that combines a corkscrew twisting motion and uterine curettage. When using this method, the device is inserted to the fundus and then withdrawn to the lower uterine segment, alternating between a corkscrew twisting motion and the motion usually used to curette the endometrium during a dilation and curettage (D&C). In a retrospective review with uniform pathology evaluation, use of a corkscrew twisting motion and uterine curettage yielded adequate tissue in 95 percent of cases, which was higher than the 77 percent success rate with a corkscrew technique alone
- When using a suction device, do not let the sheath come outside of the external os or you will lose the negative pressure. If you do, simply expel the contents of the sheath into the formalin container or onto a sterile nonadhesive bandage (eg, Telfa), taking care not to contaminate the device, and reinsert the sheath. Multiple passes are sometimes needed to assure specimen adequacy.
- **Anesthesia:** Office sampling procedures can usually be performed without significant pain. Discomfort can be minimized by reassuring the patient, explaining each step before doing it, and avoiding use of mechanical cervical dilators and/or a tenaculum, if possible. Some clinicians recommend an oral nonsteroidal anti-inflammatory drug (NSAID) 30 to 60 minutes prior to the procedure to decrease cramping
- **Cervical preparation and dilation:** Cervical preparation or dilation is not required in many patients, particularly premenopausal parous patients. For those in whom it may be difficult to pass the sampling device without cervical dilation, misoprostol (200 to 400 mcg) orally, per vagina, or both may be given the night before the procedure
- **Endometrial brush:** Several observational studies have compared endometrial sampling results from the endometrial brush with those of an endometrial suction sampling device. In a larger study, 526 pre- and postmenopausal patients were evaluated using both the Tao Brush and the Pipelle. In the postmenopausal patients, endometrial sampling with the brush resulted in a significantly higher proportion of adequate endometrial samples compared with the suction device

8. How will you implement changes and recommendations?

- A proforma/ checklist maybe put in the procedures room and included with the endometrial biopsy histopathology request. This shall outline the precautionary measures and instructions, as well as the steps of endometrial biopsy procedure.

- The topic will be mentioned in the morning meeting.
- The topic maybe covered and illustrated in one of the biweekly scientific meetings.
- An email/ message maybe sent to all teams on the OBGYN department group.

9. Do the audit standards cover the practice of one or more professional groups?

This is a Multi-disciplinary audit

This is an Uni-disciplinary audit

10. What data collection method will be used?

Retrospective and concurrent data collection: endometrial biopsy results over the previous six months (April- September 2024) were extracted from the computer system and analysed.

After drawing recommendations and implementing changes, endometrial biopsy results over the next six months (November 2024- April 2025) will be monitored and audited.

11. What is your sample size?

Name of Service or Team and Division

Interval sampling was the method used for sample size calculation of this audit, in which all results in the specified time periods (April- September 2024) and (November 2024- April 2025) were included.

429 cases were available for the previous 6 months (April- September 2024). Which is more than the sample size required for any prevalence study assuming a 50% prevalence rate and an infinite population (n=384).

12. What is your planned project timetable

Project Activity	Estimated Completion Date
Date of completion of data collection, inputting, and analysis	31/10/2024
Proposed date for presentation of results and recommendations for the modification of practice	4/11/2024
Proposed date for start of implementation of modifications	5/11/2024
Proposed date for re-auditing the results	May 2025

13. How will service users or carers be involved in this audit?

Service users are not involved in this audit since they cannot modify/ control patient factors for insufficient endometrial biopsy results (example: nullipara, menopausal, .. etc)

Project lead:

Project supervisor:

[figure not shown]
[figure not shown]
[figure not shown]
Department head:

Outpatient endometrial sampling checklist

Before starting the procedure:		✓
1.	Patient identity checked Informed consent obtained Equipment checked Proper lithotomy position and exposure.	
2.	No contraindications: pregnancy, acute PID, bleeding diathesis, or obstructing cervical lesion	
3.	Bimanual examination performed with non-sterile gloves, paying particular attention to the position of the cervix, and size and orientation of the uterus.	
During the procedure:		✓
4.	Insert an appropriate-size speculum to visualize and center the cervix	
5.	Optional: Cervix cleansed with antiseptic solution (especially if profuse vaginal discharge)	
6.	Optional: Tenaculum applied in horizontal orientation (especially if cervix is very mobile or cervicouterine angle is very marked (uterus not axial), or dilation/ sounding is needed). An Allis/ Vulsellum is a better alternative (less pain and bleeding)	
7.	Pipelle slowly introduced through the cervical os on to the uterine fundus using moderate and steady pressure. Stopped when resistance is met. Pipelle should be inserted 6-8cm to ensure that it is properly placed inside the uterus	
8.	Sheath stabilized the with one hand and piston pulled out as far as possible to create suction	
9.	Device tip moved along the endometrial surface using a corkscrew (360°) rotation combined with a repeating cephalic-caudal motion while maintaining suction. Combining corkscrew motion with the motion usually used to curette the endometrium during D&C improves the sample adequacy	
10.	Contents expelled into formalin container once the sheath comes out of the external os, taking care not to contaminate the device tip with non-sterile formalin or container.	
11.	Second or multiple passes done to ensure sample adequacy	
After the procedure:		✓
12.	Check side effects: Vasovagal attacks are self-limiting, keep in supine. Painful uterine cramps usually resolve in 12 hours. Bleeding points in cervix controlled with cotton pressure or silver nitrate sticks.	
13.	Patient counselled about red flags: come back if persistent pain, heavy vaginal bleeding, offensive vaginal discharge, fever, and chills.	

Name:

Date:

(A) Endometrial biopsy catheter is inserted into the uterine fundus until resistance is felt. (B) The internal piston is fully withdrawn once the catheter is in the uterine cavity. (C) A 360-degree rolling or twirling motion is used as the catheter is moved between the uterine fundus and the internal os of the cervix

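### Does letting the checklist travel with the histopathology request bias the before-and-after comparison of sample adequacy?

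*Protocol*

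**What the plan says.** Section 8 of the Protocol lists four measures: a checklist, a mention at the morning meeting, possible coverage at a biweekly scientific meeting, and a possible message to the department's teams. On the checklist it says: "A proforma/ checklist maybe put in the procedures room and included with the endometrial biopsy histopathology request". The next sentence describes its content: "This shall outline the precautionary measures and instructions, as well as the steps of endometrial biopsy procedure".

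The form printed at the end of the Protocol has 13 items, a tick column, and lines for name and date. Item 9 states that combining two sampling motions "improves the sample adequacy". Item 11 records that repeat passes were made for the sake of adequacy.

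The outcome is described in Section 5. The baseline insufficiency figure of 32% comes from "a retrospective analysis of all outpatient endometrial samples sent to the histopathology department". Under Section 10, the comparison period is defined by the statement that "endometrial biopsy results over the next six months (November 2024- April 2025) will be monitored and audited". Section 12 gives 5/11/2024 against "Proposed date for start of implementation of modifications".

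**The concern.** The plan compares adequacy before and after a change in practice, so adequacy should be judged in the same way in both periods. Section 8 allows the intervention's own form to accompany the paperwork sent to the department whose reports supply the outcome. The form is laid out to be filled in, two of its items mention sample adequacy, and it did not exist at baseline. A pathologist who read it in the re-audit might judge a borderline sample differently. Part of any observed change would then come from the assessment and not from the sampling. An analysis plan could not undo such a cue once it had been given, so the question properly belongs to Section 8.

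**Working it through.** **1. Could the form reach one period only?** Yes. Baseline is April to September 2024 (Sections 10 and 11). Section 5 says April to October. On either reading every baseline sample predates 5/11/2024, so 0 of the 429 cases reported for April to September could carry the form. The re-audit window has 30 + 31 + 31 + 28 + 31 + 30 = 181 days, and 181 − 4 = 177 of them fall on or after 5 November (177/181 = 97.8%). These counts show opportunity. They do not measure an effect, and they assume that an optional measure starts on its proposed date.

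**2. What must happen for bias to arise?**

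| Step | What the Protocol says |
|---|---|
| The form is attached to requests | Optional wording in Section 8 |
| It travels completed, not blank | Not stated; Section 8 describes an outline of instructions, while the layout (ticks, name, date) suggests completion |
| It reaches the reporting pathologist, not only specimen reception | Not stated |
| The pathologist reads it | Not stated |
| It changes an adequacy call | Not stated; that the pathologist makes this call is itself implied, not written |

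**3. How informative is the cue?** Item 9's remark about adequacy is fixed print, the same on every form, and says nothing about a particular specimen. Item 11 is the nearest to case-level information, but it records what the operator did and not whether tissue was obtained. Other items cover identity, consent, side effects and counselling (items 1, 12 and 13), which concern the operator and the patient.

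**4. How large would an effect have to be?** The Protocol gives no reclassification rate, so this is illustration only. Assume 429 cases in each period, no true change from 32%, and a share r of truly insufficient re-audit samples called adequate. The apparent re-audit rate is p₂ = 0.32 × (1 − r). The number reclassified is r × 429 × 0.32 = r × 137.28. The expected test statistic is z = (0.32 − p₂) / √{[0.32 × 0.68 + p₂(1 − p₂)] / 429}.

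| r | Samples reclassified | Apparent rate | Expected z |
|---|---|---|---|
| 5% | 6.9 | 30.4% | 0.51 |
| 10% | 13.7 | 28.8% | 1.02 |
| 20% | 27.5 | 25.6% | 2.08 |
| 30% | 41.2 | 22.4% | 3.18 |

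For r = 20%: p₂ = 0.32 × 0.80 = 0.256, and z = 0.064 / √[(0.2176 + 0.1905) / 429] = 0.064 / 0.0308 = 2.08. The corresponding chances of a nominally significant fall (two-sided 5% test) are about 7%, 17%, 54% and 89%. About one in five insufficient samples would have to be called adequate before the expected statistic passed 1.96. A cue could also work the other way: calling 5% of adequate samples insufficient would give 0.32 + 0.68 × 0.05 = 35.4%. Nothing in the Protocol favours any row, or either direction.

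**5. What would withholding the form achieve?** It would remove one possible cue. The pathologist would still know the date of every specimen and hence the audit period. The cost is a filing step and possibly lower completion of the checklist, which is the measure being introduced.

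**The case for a change.** The best case for a change is that the risk is easily avoided. The checklist acts on the operator, and nothing in the Protocol says that the pathologist needs it. The tick column and the name and date lines do point to a completed form. Any influence would fall in one period only, and one sentence would close the gap. This stands as a reason for sensible handling on the ground. It does not show that anything in the plan is wrong, because it establishes an open detail and not a bias.

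Two supporting arguments do not stand. The first is that the plan sets its own standard by citing evidence obtained "In a retrospective review with uniform pathology evaluation". Those words describe the source of the 95 versus 77 percent adequacy comparison in Section 7. The plan does not adopt them as a rule for itself, and they need not mean that pathologists saw identical paperwork. The second is that the checklist is the only route by which histopathology could learn of the project. The message is addressed to one department ("An email/ message maybe sent to all teams on the OBGYN department group"), but attendance at the two meetings is not described, so the argument rests on silence.

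**Conclusion.** No change to the plan is needed. Section 8 leaves the routing of an optional form unspecified. It states no rule or figure that yields a wrong result, and no passages conflict on the point. If completed forms did reach the reporting pathologist, there would be a small risk of differential adequacy assessment, of unknown direction and size, on top of the pathologist's existing knowledge of the calendar period. That judgement assumes that the form serves mainly as a prompt for the operator, as the sentence describing its content suggests, and that its printed text carries little about any one specimen. Evidence that pathologists used completed forms when calling samples adequate would reopen the question. The Protocol contains none, and the audit lead can decide where completed copies are kept without amending the plan.

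### Does the n = 384 benchmark in section 11 leave the before-after comparison without a sample-size basis?

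*Protocol*

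**What the plan says.** Section 5 of the protocol gives the starting point and the aim. A retrospective review "from April- to October 2024 study showed an insufficient sample percentage of 32" per cent. The published range is given as "Insufficient samples are obtained in 5-23% of cases". The project is to identify the causes, act on them, and close with "finally e-auditing the endometrial biopsy results after six months".

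Section 10 defines the two windows. The baseline is April to September 2024, and for the follow-up "endometrial biopsy results over the next six months (November 2024- April 2025) will be monitored and audited".

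Section 11 answers the sample-size question in two parts. It first says that every result from both windows is included. It then remarks that "429 cases were available for the previous 6 months (April- September 2024"), and continues: "Which is more than the sample size required for any prevalence study assuming a 50% prevalence rate and an infinite population (n=384"). It states no confidence level or margin of error for the 384, no target reduction, no power and no expected count for the re-audit.

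**The concern.** The project asks whether the insufficient-sample rate falls between two periods. The one numerical benchmark in section 11 concerns a different quantity, the precision of a single proportion, and it is compared with the first period alone. A reader could take "429 exceeds 384" as assurance that the re-audit can tell improvement from chance, which it does not show. The reference to any prevalence study is also too wide, because a tighter margin would need far more than 429 cases.

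What would be at stake is interpretation. If a real fall of a few points produced an inconclusive re-audit, it might be read as failure. The inputs also look unsettled: section 5 attaches the 32% to a period running to October, while sections 10 and 11 stop at September.

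**Working it through.** **Inputs.** From section 5: baseline rate 32%, literature range 5-23%. From section 11: 429 baseline cases, assumed prevalence 50%, n = 384. Not in the document, so assumed here: 95% confidence, two-sided 5% test, independent samples, and a re-audit count varied from 200 to 500.

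**Step 1: reproduce 384.** For one proportion, n = z² p(1−p)/d².

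- p = 0.50, d = 0.05, z = 1.96: 3.8416 × 0.25 / 0.0025 = 384.2, which matches the plan.
- d = 0.04: 600. d = 0.03: 1,067.
- d = 0.05 at 90% confidence: 271. At 99% confidence: 663.

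Of the combinations tried, only 95% confidence with a margin of 5 points gives 384. The arithmetic is right, but the words about any prevalence study hold only for that margin or a wider one.

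**Step 2: what 429 gives for the baseline rate.** Half-width = 1.96 × √(p(1−p)/429).

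- p = 0.50: 4.7 points.
- p = 0.32: 1.96 × √(0.2176/429) = 4.4 points.

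As a statement about the baseline estimate, the claim is true.

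**Step 3: what the two windows give for the change.** Half-width = 1.96 × √(0.32 × 0.68/429 + p₂(1−p₂)/n₂). With n₂ = 429 and p₂ = 0.23 this is 1.96 × √(0.3947/429) = 5.9 points. With p₂ = 0.32 it is 6.2 points.

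Power uses the two-proportion z test with pooled variance under the null. For 32% to 23% with 429 in each period, the pooled rate is 0.275 and the null standard error is √(2 × 0.275 × 0.725/429) = 0.0305. The standard error under the alternative is 0.0303. Power is Φ((0.09 − 1.96 × 0.0305)/0.0303) = Φ(1.00) = 84%.

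| Re-audit cases (assumed) | 95% half-width of change, points | Smallest fall with 80% power, points | Power to 27% | to 25% | to 23% | to 20% |
|---|---|---|---|---|---|---|
| 200 | 7.3-7.8 | 10.7 | 24% | 43% | 64% | 89% |
| 300 | 6.5-6.9 | 9.4 | 30% | 54% | 76% | 95% |
| 429 | 5.9-6.2 | 8.6 | 36% | 62% | 84% | 98% |
| 500 | 5.8-6.0 | 8.2 | 39% | 66% | 87% | 99% |

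With 429 cases before, a fall to 23% reaches 80% power at about 352 re-audit cases. With equal periods it needs 386 in each. If the true baseline were 30% or 34%, power to detect 23% with 429 in each period would be 64% or 95%.

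**Step 4: does 384 determine anything?** The number analysed is whatever the hospital produces in two fixed six-month windows. Replacing 384 with a two-sample figure would add or remove no case. No rule in the document depends on passing 384.

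**Step 5: the baseline months.** Sections 10 and 11 both give April to September and both call it six months. Counted inclusively, April to October is seven. The plan was completed on 27/10/2024, before October ended. The section 5 wording is therefore most likely a slip, or means up to the start of October.

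**The case for a change.** The strongest case for a change is that section 11 chose to give a numerical argument, and that argument is aimed at the wrong quantity. Taking all cases does not remove chance variation when two periods are compared to judge whether practice improved. A 5-point fall, from 32% to 27%, has at most 39% power across the re-audit counts considered, so it would more often be missed than found. Nothing in the section warns of this. The cost of saying so is one reworded paragraph.

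Much of this stands. The figure 384 is a one-sample figure, the margin behind it is unstated, and "any prevalence study" claims too much. What does not follow is that the plan is wrong about its comparison. The sentence speaks only of prevalence, and the document nowhere says that 429 is adequate for detecting a change. It adopts no significance test and does not say that an inconclusive re-audit would count as no improvement. The low powers come from targets that the document does not set (25%, 27%) or from re-audit counts of 200 to 300, for which it gives no basis. The precision of the change and the reading of a modest result are matters that a protocol commonly leaves to the analysis plan, which is not at hand. Only the baseline count could be checked, because the plan predates the re-audit window.

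**Conclusion.** No change to the plan is called for. The 384 remark is a correct benchmark for the baseline rate, loosely worded, attached to a design whose size is set by the calendar. Correcting it would leave the cases collected, the comparison and the result as they are. An analyst who reports the two rates with a confidence interval for the difference will show the precision directly.

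The windows are also reasonable for the only external yardstick in the document. Assuming a 32% baseline, independent samples and about 429 cases in each period, the change would be estimated to about 6 points either way, with about 84% power for a fall to the top of the 5-23% range and 98% for a fall to 20%. Smaller falls could be missed, and a re-audit with fewer than about 352 cases would have less than 80% power for a fall to 23%. That limits what an inconclusive re-audit can be taken to show, but it is no error in the plan.

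The October/September mismatch is real but clerical. Two sections agree on April to September, and the completion date makes a full October extract impossible. It does not bear on whether 384 suits the comparison.

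### Checklist item 2 screens only for acute PID, whereas Section 7 would also defer sampling for acute vaginal or cervical infection

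*Protocol*

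**What the plan says.** Section 7 of the protocol, under Contraindications, lists four conditions that bear on whether to sample:

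- Item 1, pregnancy: "The only absolute contraindication to endometrial sampling is the presence of a viable and desired pregnancy".
- Item 2, bleeding: "A bleeding diathesis is a relative contraindication since bleeding may be excessive in such patients".
- Item 3, infection: "In the presence of acute vaginal, cervical, or pelvic infection, the procedure should be deferred, if possible, until the infection has been treated". The rule is lifted where "the indication for the biopsy is to evaluate for a subclinical infection or perform microbiologic and histologic studies".
- Item 4, an obstructing lesion, which Section 7 discusses only for a narrow group: "In rare instances, in which endometrial sampling needs to be performed in a patient with cervical cancer".

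A fifth entry says that an intrauterine device does not prevent sampling, so it is not a contraindication.

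Section 8 describes the form that is to carry this into practice: "A proforma/ checklist maybe put in the procedures room and included with the endometrial biopsy histopathology request". On its content, Section 8 adds: "This shall outline the precautionary measures and instructions, as well as the steps of endometrial biopsy procedure".

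The form itself is the Outpatient endometrial sampling checklist at the end of the protocol. Its second line, to be ticked before the procedure starts, reads: "No contraindications: pregnancy, acute PID, bleeding diathesis, or obstructing cervical lesion".

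**The concern.** The checklist is the part of the plan meant for the procedures room. The operator will have item 2 in view, not Section 7. On infection, item 2 names pelvic disease and leaves out the vagina and the cervix, which Section 7 lists separately. A woman with acute vaginal or cervical infection can therefore pass the written screen although Section 7 would have her biopsy deferred if possible.

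What is at stake is procedural safety and the form's agreement with its own source. Section 7 counts pelvic infection and bacteremia among the rare complications of sampling, so the precaution has a purpose. The form does not authorise sampling in an infected woman, and a clinician may still defer. The point is only that the form does not prompt for it.

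**Working it through.** The plan gives no figure on this point to reproduce. The check is a comparison of two current texts in the same document. The protocol does not expand PID; it is read here as pelvic inflammatory disease.

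**Step 1: infection sites.** Section 7 names three: vagina, cervix, pelvis. Item 2 names one: pelvis, as acute PID. Missing: 3 − 1 = 2 (vagina and cervix).

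**Step 2: is this just abbreviation?** Compare each heading.

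| Heading | Section 7 | Checklist item 2 | Item 2 relative to Section 7 |
|---|---|---|---|
| Pregnancy | viable and desired only | any pregnancy | wider |
| Bleeding diathesis | relative contraindication | named without qualifier | same condition |
| Obstructing cervical lesion | in cervical cancer, some patients | any such lesion | wider |
| Infection | three sites, defer if possible, one exception | acute PID | narrower |

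Shortening widened two headings and left one unchanged. Infection is the only one of the four that became less cautious. Nor can acute PID stand for all three sites within this document, since Section 7 sets vaginal and cervical infection beside pelvic infection as separate entries.

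**Step 3: does another item close the gap?** The form has 13 items, of which item 2 alone screens for contraindications, leaving 13 − 1 = 12. The ones that come near the subject are:

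- Item 1: identity, consent, equipment and positioning.
- Item 3: bimanual examination, directed at the position of the cervix and the size and orientation of the uterus.
- Item 4: the speculum step, where the vagina and cervix are first seen. It gives no instruction to defer.
- Item 5: profuse discharge is a reason for optional antiseptic cleansing, after which the form goes on.
- Item 13: offensive discharge and fever appear as after-care warning signs.

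The rest cover applying a tenaculum, taking and expelling the sample, and managing side effects. Items that give vaginal or cervical infection as a reason to defer: 0 of 12.

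**Step 4: consequence.** All 13 items can be completed truthfully for a woman with acute vaginal or cervical infection and none of the four conditions listed in item 2.

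**The case against.** The strongest reply is that the source rule is soft and the form is a summary. Section 7 asks for deferral only if possible, allows an exception, and calls one other condition the sole absolute contraindication. Its contraindications stand under their own heading, apart from the steps labelled as proforma items, and Section 8 asks the form to outline precautions, not to reproduce them. Choosing what goes into a single tick-box is partly clinical judgement, and nothing says that the list in item 2 is exhaustive.

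This limits the weight of the point but does not remove the mismatch. Section 7 as a whole is headed as the background and criteria to be audited. Item 2 already lists other conditions that are only relative, so softness does not explain dropping these two sites. An operator faced with a named list will reasonably take it as the list.

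A second reply is that item 2 is ticked before the speculum goes in, so rewording it will not catch infection first seen at item 4. That stands as a limit on the fix: the new wording helps most where infection is already known or symptomatic. It is no reason to leave the sites out, because item 2 already includes an obstructing cervical lesion, which may also be found only at the speculum.

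Finally, the counts above are counts of words and items, not of risk. That is correct, and they are not offered as a measure of harm.

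**Conclusion.** The concern holds, as a minor one. The form's only contraindication screen carries one of the three infection sites in Section 7, and infection is the one heading of four on which it is narrower than its source. The conclusion rests on reading PID in its usual sense and on taking the conditions named in item 2 as the ones the operator is asked to exclude.

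No effect on the insufficient-sample rate, the sample size or the comparison of the two six-month periods is claimed. The protocol does not say how often acute vaginal or cervical infection occurs in these women, so no number affected is given.

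**What to change.** In checklist item 2, replace the acute PID entry with: acute infection of the vagina, cervix or pelvis (defer if possible until treated, unless the biopsy is intended to evaluate subclinical infection or for microbiologic and histologic studies). Leave the rest of item 2 and the other 12 items as they are.

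This brings in no outside standard; it only makes the form agree with Section 7. It can be done before the form goes into use (Section 12 proposes to start the modifications on 5/11/2024) or at the next printing. It needs no extra patients, staff, procedures or data. The only cost is a slightly longer line.
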